TREATMENT PATTERNS AND CLINICAL OUTCOMES AMONG PATIENTS RECEIVING CDK4/6 INHIBITORS COMBINATIONS FOR HR+/HER2- ADVANCED/METASTATIC BREAST CANCER IN A CANADIAN REAL WORLD SETTING

Study information

Title	Treatment Patterns And Clinical Outcomes Among Patients Receiving CDK4/6 inhibitors Combinations For HR+/HER2- Advanced/Metastatic Breast Cancer In A Canadian Real World Setting
Protocol number	A5481178
Protocol version identifier	Version 3.0
Date	13 February 2023
Active substance	Palbociclib
Medicinal product	Palbociclib (IBRANCE®; PD-0332991)
Research question and objectives	
To describe the current treatment patterns, changes over time, and clinical outcomes of adult female patients receiving palbociclib combination treatments for metastatic breast cancer in a Canadian real world setting, including demographic and clinical characteristics.
 
Primary objective
 
• To characterize real world treatment patterns among patients with hormone receptor positive/human epidermal growth factor receptor 2 negative (HR+/HER2-) - advanced/metastatic breast cancer (ABC/MBC) receiving palbociclib combination treatment

PFIZER CONFIDENTIAL

[REDACTED]

Pfizer Confidential

	PPD	MPH,	
	PPD		

This document contains confidential information belonging to Pfizer. Except as otherwise agreed to in writing, by accepting or reviewing this document, you agree to hold this information in confidence and not copy or disclose it to others (except where required by applicable law) or use it for unauthorized purposes. In the event of any actual or suspected breach of this obligation, Pfizer must be promptly notified.

[figure not shown]
PFIZER CONFIDENTIAL

[REDACTED]

2. LIST OF ABBREVIATIONS

Abbreviation	Definition
ABC/MBC	Advanced/metastatic breast cancer
AE	Adverse events
AEM	Adverse event monitoring
AI	Aromatase Inhibitor
CDK	Cyclin-dependent kinase
CDK4/6	Cyclin-dependent kinase 4 and 6
CI	Confidence Interval
COVID-19	COronaVIrus Disease 2019
CSV	Comma separated values
ECOG	Eastern Cooperative Oncology Group
EHR	Electronic health record
EMR	Electronic Medical Record
ER	Estrogen Receptor
GPP	Guidelines for Good Pharmacoepidemiology Practices
HER2	Human epidermal growth factor receptor 2
HR	Hormone receptor
IEC	Independent ethics committee
IRB	Institutional review board
IRIS	Ibrance Real world Insights Study

PFIZER CONFIDENTIAL

[figure not shown]
ISPE	International Society for Pharmacoepidemiology
LHRH	luteinizing hormone-releasing hormone
NIS	Non-interventional study
NLP	Natural language processing
NSAI	Non steroidal aromatase inhibitor
OS	Overall survival
PFS	Progression Free Survival
PR	Progesterone receptor
RCT	Randomized clinical trial
SABCS	San Antonio Breast Cancer Symposium
SD	Standard deviation
TTNT1	Length of treatment for the first line
TTNT2	Length of treatment for the second line
TTC	Time from date of ABC/MBC diagnosis to starting chemotherapy
SAP	Statistical analysis plan
VM	Virtual machine
YRR	Your reporting responsibility

4. ABSTRACT

Title: Treatment Patterns and Clinical Outcomes Among Patients Receiving CDK4/6 inhibitors Combinations For HR+/HER2- Advanced/Metastatic Breast Cancer In A Canadian Real World Setting.

Version 3.0

Date of the abstract: 13 February 2023

Main Author and affiliation:

PPD

Rationale and background: Breast cancer is the main cause of cancer death in women worldwide, with hormone receptor positive (HR+) and human epidermal growth factor receptor 2 negative (HER2-) tumours being the most commonly diagnosed. Endocrine therapy is a mainstay of breast cancer treatment. In the PALOMA clinical trials, adding palbociclib resulted in greater median progression free survival (PFS) than endocrine therapy alone. Since its approval in Canada in 2016, palbociclib has been used in patients with HR+/HER2- advanced/metastatic breast cancer (ABC/MBC), but little is known about its real world use and clinical outcomes in a Canadian setting.

[figure not shown]
Research question and objectives: The primary objective of this study is to explore patient demographics, clinical characteristics, treatment patterns and changes, and clinical outcomes of adult female patients with HR+/HER2- ABC/MBC in Canada, who received a CDK4/6i based therapy for their ABC/MBC.

Study design, study size, and population: This study will be a retrospective chart review of patient records from Sinai Health based cancer clinics. All records from female patients ≥ 18 years old with HR+/HER2- ABC/MBC diagnosed at this site between 01 January 2016 and 01 July 2021 will be used. It is estimated that there will be approximately 300 diagnoses of ABC/MBC within the study period at Sinai Health, approximately 180 of which will be HR+/HER2-. Only patients who have taken a CDK4/6 inhibitor in combination with an endocrine therapy will be included in this study. Using electronic health records (EHRs) stored within Sinai Health, natural language processing (NLP) algorithms (ie, Pentavere's DARWEN™ technology) will be trained to extract data variables from the EHR data.

Variables and data sources: NLP algorithms will be trained to extract data relevant to patient demographics, treatment patterns, treatment changes, and clinical outcomes. These variables will be extracted from structured and unstructured EHR data. The data variable rules and definitions will be developed in collaboration with Sinai Health clinicians. The use of NLP as a method of chart review is more efficient and cost-effective than manual review.

Data analysis: All analyses will be descriptive in nature and all subject to modification based on sample size and final data specifications. No inferential statistical analyses will be conducted. Categorical variables will be described using the number of observations and

PFIZER CONFIDENTIAL

number and percent (%) in each category. Numeric variables will be described using the number of observations, mean and standard deviation, and minimum, maximum, median and interquartile range. Treatment patterns and changes over time of patients on Palbociclib will be reported. Time to event will be described using an unadjusted Kaplan-Meier chart and the survival median.

5. AMENDMENTS AND UPDATES

Amendment number	Date	Protocol section(s) changed	Summary of amendment(s)	Reason
Version 3.0	13 February 2023	Section: STUDY INFORMATION	
Change of protocol version identifier from "version 2.0" to "version 3.0" and the date from "12 November 2021" to "13 February 2023"
 
Change of "Secondary objective" with the deletion of "To evaluate efficacy of current treatment for Canadian breast cancer patients using surrogates for time to next treatment in the real-world setting including:
 
• The length of treatment for the first line (TTNT1), the length of treatment for the second line (TTNT2), the time from cyclin-dependent kinase 4 and 6 (CDK4/6) inhibitor to starting chemotherapy (TTC) and overall survival (OS)• The length of treatment for short term versus long term responders" 
which is now included with the exact similar wording to the CCI [REDACTED] section, except for the following wording "...the time from cyclin-dependent kinase 4 and 6 (CDK4/6) inhibitor to starting chemotherapy (TTC)..." which was replaced by "...the time from the date of ABC/MBC diagnosis to starting chemotherapy (TTC)..."
 
Change of "The authors" section, the author and contact information of PPD [REDACTED], PhD Director of Clinical Operations and Head Scientist, PPD [REDACTED] PPD [REDACTED] is replaced by PPD [REDACTED], MPH, Clinical Program Lead, PPD [REDACTED]
	
The changes in the study information section are driven by the study protocol amendment.
 
The secondary objective was adapted as the initial planned sample size (e.g. 180 patients) will be dramatically lower than expected (less than 30% of initial sample size); CCI [REDACTED]
 
As per clinical expert insight, The definition of TTC was clarified to the time from the date of ABC/MBC diagnosis to starting chemotherapy
 
Change of staff at Pentavere (vendor) occurred: PPD [REDACTED]

PFIZER CONFIDENTIAL

			This latter change also applies to the section 3. Responsible Parties	
Version 3.0	13 February 2023	Section: LIST OF ABBREVIATIONS	Changed the definition of TTC from "Time from date CDK4/6 treatment to starting chemotherapy" to "time from date of ABC/MBC to starting chemotherapy"	This change was requested by PPD [REDACTED] as this is a more appropriate way of deriving TTC
Version 3.0	13 February 2023	Section 4: ABSTRACT	
Change from: "Version 2.0, Date of the abstract: 12 November 2021, PPD [REDACTED]"
 
To:
 
"Version 3.0, Date of the abstract: 13 February 2023, PPD [REDACTED]"
 
In the Data analysis section, first sentence changed from "Data analysis: All analyses will be descriptive in nature." to: "Data analysis: All analyses will be descriptive in nature and all subject to modification based on sample size and final data specifications"
	These changes in the abstract section are driven by the study protocol amendment.
Version 3.0	13 February 2023	Section 6: MILESTONES	
Change of date for Start of study collection from "31 January 2021" to "12 October 2022"
 
Change of date for End of data collection from "30 June 2022" to "31 March 2023"
 
Change of date for Data summary report from "28 February 2022" to "15 April 2023"
 
Change of date for Interim report from "29 April 2022" to "31 May 2023"
 
Change of date for Final study report from "31 August 2022" to "30 June 2023"
	Dates of original planned milestones had become obsolete due to significant delays, so the new milestones dates better reflect the new anticipated milestones.
Version 3.0	13 February 2023	Section 8: RESEARCH QUESTION AND OBJECTIVES	
Deletion of the following secondary objectives : "To evaluate efficacy of current treatment for Canadian breast cancer patients using surrogates for time to next treatment in real-world setting including:
 
 o The length of treatment for the first line (TTNT1), the length of treatment for the second line (TTNT2), the time from date of ABC/MBC 	The secondary objective was adapted as the initial planned sample size (e.g. 180 patients) will be dramatically lower than expected (less than 30% of initial sample size); CCI [REDACTED]

PFIZER CONFIDENTIAL

			
diagnosis to chemotherapy (TTC) and overall survival (OS)
 
o The length of treatment for short term versus long term responders
 
CCI [REDACTED]
	
Version 3.0	13 February 2023	Section 9.7: DATA ANALYSIS	Sentence "The planned data analyses are descriptive in nature." was updated to "The above planned data analyses are descriptive in nature and all subject to modification based on sample size and final data specifications"	This change is to provide further clarity on the conduction of data analyses.

6. MILESTONES

Milestone	Planned date
Start of data collection	12 October 2022
End of data collection	31 March 2023
Data Summary Report	15 April 2023
Interim report	31 May 2023
Final study report	30 June 2023

7. RATIONALE AND BACKGROUND

As the most common cancer diagnosis globally, breast cancer accounts for 1 in 4 cancer cases and 1 in 6 cancer deaths in females. In 2020, breast cancer resulted in 685,000 deaths making it the fifth leading cause of cancer deaths worldwide (1). In Canada, the age-standardized mortality rate for breast cancer has declined 48% since the 1980s, likely due to improved screening and available therapies (2). Despite this downward trend in mortality, 5 year survival rates are very different between those with stage 0-I (100%), stage II (93%), and stage III (72%) breast cancer and those with stage IV breast cancer (22%) (3).

Greater knowledge of breast cancer heterogeneity has resulted in the use of subtype classification to more accurately manage disease. Breast tumours are classified according to their expression of hormone receptors (HR) and human epidermal growth factor receptor 2 (HER2) (4). Most prevalent in breast cancer classification is HR status, by which tumours that grow in the presence of estrogen and progesterone are classified as HR positive (HR+). HR+

PFIZER CONFIDENTIAL

tumours generally respond better to endocrine therapy and people with these tumours have higher overall survival (OS) than those that are HR negative (HR-) (4). Together with HR status, HER2 status is an important feature of tumour classification, with HER2+ tumours having worse prognosis than HER2- tumours. HR+/HER2- tumours are the most commonly diagnosed subtype of breast cancer and respond well to endocrine therapy (4).

Endocrine therapies, such as letrozole and fulvestrant, are a mainstay of HR+ breast cancer treatment, sometimes in combination with other therapies. The PALOMA-1 trial evaluated palbociclib, a cyclin-dependent kinase 4 and 6 (CDK4/6) inhibitor, in combination with letrozole in patients with HR+/HER2-ABC/MBC. Palbociclib combination therapy with letrozole demonstrated median progression-free survival (PFS) of 20.2 months versus 10.2 months in patients receiving letrozole and placebo (5). These results were confirmed by the success of the phase III PALOMA-2 study, in which palbociclib and letrozole combination treatment demonstrated greater median PFS than letrozole and placebo (24.8 months and 14.5 months, respectively) (6). In cases of disease progression despite initial endocrine therapy, the PALOMA-3 trial demonstrated that palbociclib combination with fulvestrant resulted in median PFS of 9.2 months compared to 3.8 months in those receiving fulvestrant and placebo (4,7). Currently, palbociclib is indicated for use in combination with any aromatase inhibitor or fulvestrant for those with HR+/HER2- ABC/MBC (8).

Understanding the effectiveness of new treatments in a diverse clinical practice as a complement to randomized clinical trial (RCT) data is important as this provides evidence of the clinical benefit of these treatments in a more heterogeneous population with comorbid conditions and variations in care delivery seen in routine clinical practice. Real-world outcomes for patients with ABC/MBC who were treated with palbociclib in combination with an aromatase inhibitor (AI) or fulvestrant have been reported in several publications and at medical congresses. A comparative effectiveness analysis of palbociclib + letrozole versus letrozole alone was presented at the San Antonio Breast Cancer Symposium (SABCS) 2019 congress and subsequently published. Using the Flatiron Health Analytics Database, a total of 1,430 female patients with HR+/HER2-MBC in the first-line setting were included in the analysis demonstrating an adjusted HR for PFS of 0.58 (95% confidence interval(CI), 0.49-0.69; $P < 0.0001$), and an adjusted HR for OS of 0.66 (95% CI, 0.53-0.82; $P = 0.0002$) (9). From a Canadian perspective, another study reported on the Ibrance® Real World Insights Study (IRIS) involving medical chart review of 247 patients with ABC/MBC treated with palbociclib in combination with either AI (n=212) or fulvestrant (n=33) (10). The 12-month progression-free rate was 90.3% for patients treated with palbociclib + AI and the 6-month progression free survival rate was 91% for those treated with palbociclib + fulvestrant. The 12-month survival rates were 95.6% for palbociclib + AI and 100% for palbociclib + fulvestrant (10).

Palbociclib has been used in Canada since its initial approval by Health Canada in 2016, and there remains a need to better understand treatment patterns and outcomes in practice for Canadian patients with a longer follow-up. Real world data is necessary to understand these

trends and subsequent clinical outcomes to inform future treatment decisions in the HR+/HER-ABC/MBC population.

8. RESEARCH QUESTION AND OBJECTIVES

To describe current treatment patterns, changes over time, and clinical outcomes of adult female patients receiving palbociclib combination treatments for metastatic breast cancer in a Canadian real world setting, including demographic and clinical characteristics.

Primary objective

- To characterize real world treatment patterns among patients with HR+/HER2-ABC/MBC receiving palbociclib combination treatment (non steroidal AI (NSAI) [letrozole or anastrozole], or fulvestrant)

Secondary objectives

- To determine pre- and post-CDK4/6i treatment patterns and sequencing in ABC/MBC patients

CCI

A large rectangular area of the page is completely blacked out, indicating redacted content. The word 'CCI' is printed in red at the top left corner of this redacted area.

9. RESEARCH METHODS

9.1. Study design

This study will be a retrospective chart review of structured and unstructured data from EHRs stored at Sinai Health. Pentavere's DARWENT™ technology will be trained to extract data variables from the structured and unstructured EHR data (Table 1). The data variable rules and definitions will be pre-defined in collaboration with Sinai Health clinicians. Once the data variables are extracted from the EHRs, descriptive analyses will be conducted.

Data extracted will include characteristics of the patient population, comorbidities, treatment sequence, and treatment outcomes of those with HR+/HER2- ABC/MBC receiving palbociclib combination therapy.

9.2. Setting

The study period will extend from 01 January 2016 to 01 October 2021 (Figure 1). All female patients who are ≥ 18 years of age and are diagnosed with HR+/HER2- ABC/MBC and received a CDK4/6 inhibitor at Sinai Health during the study period will be included in the study. It is estimated that there will be approximately 300 diagnoses of ABC/MBC within the study period at Sinai Health, of which approximately 180 will be HR+/HER2-. Follow-up data from EHRs will be included up to the extent that they are available within the study period. Pre-index data (stage at initial breast cancer diagnosis, treatment being received at ABC/MBC diagnosis) may be extracted from EHRs up to 12 months before the index date.

[figure not shown]

Figure 1. Study Design Flow Chart

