9.2.1. Inclusion criteria

Patients must meet all of the following inclusion criteria to be eligible for inclusion in the study:

1. ≥ 18 year old female
2. HR+/HER2- breast cancer diagnosis with confirmed metastatic or advanced disease
3. Diagnosed with ABC/MBC between 01 January 2016 and 01 July 2021
4. Treatment with CDK4/6 inhibitor

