9.3. Variables

Table 1. List of study variables to be extracted (where feasible)

Variable	Role	Data source(s)	Operational definition
Patient demographics	Baseline characteristic, potential confounder, sub-group identifier	Patient EHR	
• Date of birth• Sex• Date of death
Clinical characteristics	Baseline characteristic, potential confounder, sub-group identifier	Patient EHR	
• Date of ABC/MBC diagnosis• Age at ABC/MBC diagnosis (years)• ECOG performance score at index date (0, 1, 2, 3, 4)• ESAS• Date of last follow-up• Organ level metastatic sites (bone, brain, lungs, liver; number of sites)• Tumour stage at initial breast cancer diagnosis (I, II, III, IV, Unknown)• Tumour grade• Tumour histology• ER and PR receptor status (Positive, Negative, Unknown)• HER2 status (Positive, Negative, Unknown)• Concomitant LHRH agonists
Comorbidities	Baseline characteristic, potential confounder, sub-group identifier	Patient EHR	
• Atrial fibrillation• Hypertension• Coronary Artery Disease/Myocardial infarction/Angina• Diabetes Mellitus• Stroke
Treatments	Exposure	Patient EHR	
• Systemic Therapies (therapy start and stop date including combination therapies, and line of therapy)• Surgeries• Radiation Treatment
Clinical outcomes	Outcome	Patient EHR	
• TTNT1• TTNT2• TTC• Overall Survival (landmark 3y)

ECOG, Eastern Cooperative Oncology Group; EHR, Electronic Health Record; ER, Estrogen Receptor; ESAS, Edmonton Symptom Assessment System; HER2, Human Epidermal Receptor Growth Factor 2; LHRH, Luteinizing Hormone-Releasing Hormone; PR, Progesterone Receptor; TTC, time from date of ABC/MBC to starting chemotherapy; TTNT1, length of treatment for the first line; TTNT2, length of treatment for the second line

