9.4. Data sources

Patients will be selected with dates of diagnosis of HR+/HER2- ABC/MBC between 01 January 2016 and 01 July 2021. Study data will be extracted from Sinai Health EHRs up to 12 months before ABC/MBC diagnosis until the end of the study period (01 October 2021, [Figure 1](#)).

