1 AMENDMENTS FROM PREVIOUS VERSION(S)

Amendment number	Date	SAP section(s) changed	Summary of amendment(s)	Reason
Version 2.0	2023-02-16	Title page	Change of protocol version identifier from "version 1.0" to "version 2.0" and the date from "2021-11-22" to "2023-01-24" and the author from PPD	SAP information has been updated. Change of staff at PPD
Version 2.0	2023-02-16	2.2 STUDY OBJECTIVES and 5.1 EFFICACY AND ENDPOINT(S) and 7.2 STATISTICAL ANALYSES	Change of "Secondary objective" with the deletion of "To evaluate efficacy of current treatment for Canadian breast cancer patients using surrogates for time to next treatment in the real-world setting including: 
• The length of treatment for the first line (TTNT1), the length of treatment for the second line (TTNT2), the time from cyclin-dependent kinase 4 and 6 (CDK4/6) inhibitor to starting chemotherapy (TTC) and overall survival (OS)• The length of treatment for short term versus long term responders" which is now included with the exact similar wording to the CCI section, except for the following wording "...the time from cyclin-dependent kinase 4 and 6 (CDK4/6) inhibitor to starting chemotherapy (TTC)..." which was replaced by "...the time from the date of ABC/MBC diagnosis to starting chemotherapy (TTC)..." in addition.	The secondary objective was adapted as the initial planned sample size (e.g., 180 patients) will be dramatically lower than expected (less than 30% of initial sample size); consequently, CCI As per clinical expert insight, the definition of TTC was clarified to the time from the date of ABC/MBC diagnosis to starting chemotherapy

PFIZER CONFIDENTIAL

Amendment number	Date	SAP section(s) changed	Summary of amendment(s)	Reason
			
“...last known activity” was replaced by “date of last follow-up or death”
 
These updates have been made throughout the document.
	

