7 STATISTICAL METHODOLOGY AND STATISTICAL ANALYSES

7.1 STATISTICAL METHODS

The following analyses are expected to be conducted in R.

Analyses for continuous Data

Continuous variables will be described by the number of patients with valid/non-missing observations using mean, standard deviation (SD), quantiles (Q1, median, Q3), minimum and maximum.

Analyses for Categorical Data

Categorical variables will be described by frequencies and related percentages.

Analyses for time to event end points.

Time to event variables will be analyzed using Kaplan-Meier curves (TTNT1, TTNT2, TTC, OS). Numbers at risk and cumulative incidence will be reported for each curve.

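### Overall survival rests on deaths recorded in one site's chart, so any death before the cut-off that the chart missed becomes a censoring and pushes the exploratory OS estimate up

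*Protocol*

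**What the plan says.** The study is a "retrospective chart review of structured and unstructured data from EHRs stored at Sinai Health" (Protocol 9.1). Table 1 in Protocol 9.3, repeated in SAP 5.5, gives the patient's electronic record as the data source for date of death, date of last follow-up and "Overall Survival (landmark 3y").

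Patients enter if "Diagnosed with ABC/MBC between 01 January 2016 and 01 July 2021" (Protocol 9.2.1). Data are extracted "until the end of the study period (01 October 2021") under Protocol 9.4, and Protocol 9.2 adds: "Follow-up data from EHRs will be included up to the extent that they are available within the study period". No readable text plans an outside source of deaths or a check that deaths are complete.

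SAP 7.1 states: "Time to event variables will be analyzed using Kaplan-Meier curves (TTNT1, TTNT2, TTC, OS"). Protocol 9.7 leaves the censoring rules to the SAP. There, the endpoint text in 5.1 and the time-to-event text in 7.2 are largely redacted. What can be read is the amendment table in SAP section 1, where "date of last follow-up or death" replaces an older phrase, with a note that the updates run through the whole document.

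SAP 7.2.2 labels OS exploratory. OS curves are planned by treatment type (Figures 9 and 13) and by diagnosis before or during the pandemic (Figure 17).

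**The concern.** A patient who leaves the clinic and dies elsewhere, with no entry in this site's record, leaves only a last visit. Under the readable wording she is censored there, probably not long before death. Kaplan-Meier then assumes that she has the same prognosis as the patients still followed, which is wrong for exactly these patients.

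Nothing else in the readable plan catches this. SAP section 6 completes partial dates, but here there is neither a date nor a known event. Protocol 9.9 expects little misclassification because the extraction algorithms are validated, yet accurate extraction cannot recover a death that the chart never held. Section 9.9 names several biases but not missed deaths or loss to follow-up.

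At stake is how OS and the 3-year figure are read. A reader could not tell good survival from unseen deaths, and neither a number at risk nor a confidence interval would show the difference.

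**Working it through.** The plan states no OS estimate, event count or death-capture rate, so there is no figure to reproduce. The check concerns direction and plausible size.

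**Inputs from the documents**
- Diagnosis from 01 January 2016 to 01 July 2021: 2,008 days, about 66 months. Cut-off 01 October 2021: about month 69.
- Three years of potential follow-up requires diagnosis by 01 October 2018, which is 1,004 days in. Under uniform accrual, 1,004/2,008 = 50% of patients qualify.
- Expected size is below 30% of 180, and 0.30 × 180 = 54, so at most 53 patients.
- Survival range, assuming exponential survival: 5-year stage IV survival of 22% (Protocol section 7) gives 0.22^(3/5) = 40.3% at 3 years; 12-month survival of 95.6% (same section) gives 0.956^3 = 87.4%. The illustrative 60% and 75% lie inside this range.

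**Assumptions, not in the documents:** the share m of deaths unseen (0 to 40%), and the gap between last visit and death or cut-off.

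**Formula.** If an unseen death is censored at about the time of death, the hazard of recorded death is (1 − m) times the true hazard, so Kaplan-Meier estimates S^(1−m):

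| True 3-year OS | m = 10% | m = 20% | m = 40% |
|---|---|---|---|
| 40.3% | 44.1% | 48.3% | 58.0% |
| 60% | 63.1% | 66.5% | 73.6% |
| 75% | 77.2% | 79.4% | 84.1% |
| 87.4% | 88.6% | 89.8% | 92.2% |

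**Visit lag.** Censoring everyone without a recorded death at a last visit 0 to 4 months before death or cut-off discards follow-up time in which those patients were alive. This pulls the estimate down slightly. Simulation (uniform diagnosis over 66 months, cut-off at month 69, exponential survival) for true 60%:

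| Unseen deaths | Estimate under the readable rule |
|---|---|
| 0% | about 59% |
| 10% | about 62% |
| 20% | about 65% |
| 40% | about 72% |

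**Sampling error.** The SD of the 3-year estimate is about 7 to 8 points at N = 53 for true OS of 60% to 75%. The bias is therefore smaller than one SD at 10% and 20% unseen (about 2 and 5 points) and larger at 40% (about 12 points).

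**Testing the remedy.** Suppose later chart entries confirm all survivors alive but reveal no extra deaths. The main curve for true 60% then rises from about 65% to 66% at 20% unseen, and from about 72% to 73% at 40%, because the offsetting lag has gone. Treating the patients still unknown as dead at last contact returns about 60%, 75% and 87% for those true values.

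**The case against.** The strongest reply is that the bias needs deaths the site failed to record, and no document says that there are any. Both structured and unstructured notes are read, and Protocol 9.8 describes the extraction engine as drawing on records from different systems. With complete capture and a mean visit lag of 3 months, the bias even reverses: 40.3% reads 38.3% and 87.4% reads 86.6%. At 90% capture with that lag, 87.4% reads 87.8%. This stands. A reader might infer that OS *is* overstated; the documents support only that it will be if deaths are missed.

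A reader might also infer that the cut-off biases OS. It does not: ending observation on a fixed calendar date is administrative censoring. Only unrecorded deaths before that date matter.

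Nor can it be said that the SAP lacks a censoring rule. The relevant text is redacted and may hold more, and the amendment table does not tie the readable phrase to OS alone.

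The plan also helps in part: date of last follow-up is collected, numbers at risk are reported, and Protocol 9.9 promises the proportion missing for key variables. But an unseen death does not appear as a missing value; it looks like an ordinary censored patient.

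Finally, OS is exploratory, descriptive and untested. That limits the weight of the point without removing it.

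**Conclusion.** The point holds conditionally. With a single-site chart as the only listed source of deaths, and observation ending at last follow-up or death, each unrecorded death before 01 October 2021 becomes an informative censoring that moves OS upwards. For true 3-year OS of 60%, the net error runs from about 1 point low with no deaths unseen to about 2, 5 and 12 points high with 10%, 20% and 40% unseen. These figures assume exponential survival, uniform accrual, a last visit 0 to 4 months before death or cut-off, and a censoring rule that matches the readable phrase. The unseen share is unknown.

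At 10% to 20% unseen the error is below the sampling SD, but it is systematic and would not shrink with more patients. The treatment-pattern objectives, primary and secondary, are untouched. It is worth correcting because the correction is cheap and the reader otherwise has no means of judging the OS curve.

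**What to change.** 1. In the SAP, report the number of patients with no recorded death and no contact in the last 3 months before the cut-off.
2. In Protocol 9.4 and the SAP, allow chart entries after 01 October 2021 to be read for vital status only. Data collection starts on "12 October 2022" and ends on 31 March 2023, some 12 to 18 months after the cut-off, so such entries may exist. Count deaths dated on or before the cut-off, and censor patients with later contact at the cut-off.
3. Always show, beside the main OS curve, a bounding curve that treats patients whose status is still unknown as dead at last contact. Step 2 alone cannot find deaths the chart never recorded and may raise the main curve. Present the second curve as a lower bound, since some of these patients may simply have moved their care.
4. Name possible missed deaths in Protocol 9.9.

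The cost is a protocol and SAP amendment, with prospective ethics approval under Protocol 10.3 because the vital-status read widens the extraction window; a check of fewer than 54 charts; and one extra curve. The lower bound may look less favourable than the main estimate.
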